##### **14.3.1.2 Secondary variables of the prospective cohort**

- \* DOR , DCR (CR+PR+SD) at 3, 6, 9, 12, 18, 24, 36 months
- \* Patient experience, functional status, QoL and pain, in a real-world setting for patients with advCSCC at 3, 6, 9, 12, 18, 24 and 36 months
- \* Safety data on study participants defined on paragraph 13
- \* Characteristics of patients who receive Cemiplimab as treatment for advCSCC in a real-world setting
- \* OS defined as duration from current mCSCC or ladvCSCC diagnosis and also from the initiation of each LOT until death or end of follow up
- \* Proportion of patients surviving at month 3, 6, 9, 12, 18, 24 and up to months 36 from initiation of systemic therapy

- \* PFS defined as time from first documented systemic cemiplimab therapy initiation until progression or treatment discontinuation due death or end of follow up
- \* Patient demographics and baseline characteristics (incl. age, performance status etc.) at study entry
- \* Characterization of Cemiplimab usage patterns
- \* Cemiplimab treatment regimen (initial dose and date of initiation and regimen changes)
- \* Treatment prior to and post Cemiplimab treatment, incl. surgery, radiation, systemic therapies incl. agents administered, dose, frequency and duration
- \* Surgery post initiation of Cemiplimab treatment
- \* DOT
- \* TNM stage (AJCC or UICC)
- \* Observed rates, reasons and timing of the discontinuation of Cemiplimab
- \* TTF including lack of response and discontinuation due to AE
- \* Change in patient reported QoL as per EORTC-QLQ-C30 QoL questionnaire during treatment with Cemiplimab (for prospective cohort only)

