#### **Prospective cohort:**

Each patient will be initially treated with Cemiplimab and documented during a follow up time of 36 months. Documentation will be performed up to 8 times (D1: Baseline, D2: after approx. 3 months, D3: after approx. 6 months, D4: after approx. 9 months, D5: after approx. 12 months, D6: after approx. 18 months, D7: after approx. 24 months, D8: after approx. 36 months / End of the Study). In case of Cemiplimab treatment discontinuation at any time, the documentation will continue until D8 or patient's death to assess outcome and further therapeutic modalities.

The prospective cohort of this observational study plans to collect patients with mCSCC – defined as patients with local/regional (nodal metastasis, field cancerization ect.) as well as distant metastasis (also distant lymph-node), and advCSCC – defined as patients that could not be cured either by curative surgery, curative radiotherapy or both based on a decision of an interdisciplinary tumor board. These patients will receive treatment with Cemiplimab within their clinical routine treatment.

At each participating study site, all advCSCC patients who will initiate treatment with Cemiplimab in a real-world setting will be eligible to participate in the study until the enrollment goal is achieved. The decision to prescribe Cemiplimab will be based solely on the treating physician's clinical judgment. Patients who meet inclusion criteria according to SmPC of Cemiplimab and have signed the ICF will be included in the study.

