## **7.2 DURATION OF STUDY PARTICIPATION FOR EACH PATIENT**

In the prospective cohort the data will be recorded during a follow-up of 36 months, beginning after study inclusion.

In the retrospective cohort we will document at one time point patients not intended for Cemiplimab therapy, who were first diagnosed advCSCC between Jan/2012 and Aug/2019. QoL data will be collected from patients within the prospective cohort. It is planned to perform yearly interim analyses and a final report at the end of the study.

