### 8.2 INCLUSION CRITERIA

Prospective cohort:

- Planned treatment for advCSCC adult patients  $\geq 18$  yrs who are at the first time initiated on Cemiplimab treatment according to SmPC of Cemiplimab
- Able to understand and complete study-related questionnaires
- Signed ICF

Retrospective cohort:

- Patients  $\geq$  18 years with advCSCC first diagnosed between Jan/2012 and Aug/2019
- From these patients only anonymous data will be collected. Thus no Sanofi-ICF is needed. This procedure allows including data from patients who are no longer alive (planned).

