### PARAMETER AND DEFINITIONS for the CRF's

Outcome(s)	Specific parameter	Definition	Record in Visit (month)
Clinical outcomes	Mortality, all cause, advCSCC related, and date of death	Defined as death due to all cause or disease related	-
	OS from diagnosis	Defined as time from 1 st Cemiplimab treatment until death from any cause, censoring for date of most recent follow-up in surviving patients	-
	Progression	Defined as documented in medical records	3,6,9,12,18,24,36
	Date of progression	Defined as date of first documented progression in the medical record	3,6,9,12,18,24,36
	Time to next treatment (TTNT)	Defined as time from start of Cemiplimab treatment to the start of next systemic therapy or death	-
	PFS	Defined as documented start of systemic Cemiplimab therapy until disease progression or death	3,6,9,12,18,24,36
	Patient		male / female

characteristics	Gender		
	Nationality		Baseline
	Year of birth		Baseline
	Skin phototype	Defined as Type 1, 2.....6	Baseline
	Informed consent		Baseline
	Comorbidities	Auto-immune-disease, hematologic disease, severe cognitive impairment, etc.	Baseline and 3,6,9,12,18,24,and 36
	Quality of life data (QoL)	Questionnaire: EORTC – QoL Core 30	Baseline and 3,6,9,12,18,24,and 36
	Pain	Questionnaire: EORTC – QoL Core 30	Baseline and 3,6,9,12,18,24,and 36
	Adverse events (AE) Quality of life data Reasons for discontinuing therapy Frequency of administration	Defined event as yes/no (specify, related/unrelated to anticancer therapy, serious/non-serious as documented in medical records NOTE: We will limit data collection to Common Terminology Criteria for AE (CTCAE)5.0 as documented in the medical record.Questionnaire: EORTC – QoL Core 30  Defined as lack of response, disease progression, toxicities, side effects, therapy completion, patient decision, death, other (specify) Defined as every day (QD), twice a day (BID), every week (QW), every other week (Q2W), every three weeks (Q3W), every four weeks (Q4W), other	Baseline and 3,6,9,12,18,24,and 36
	Adverse events (AE)	Defined event as yes/no (specify, related/unrelated to anticancer therapy, serious/non-serious as documented in medical records NOTE: We will limit data collection to Common Terminology Criteria for AE (CTCAE) 5.0 as documented in the medical record.	Baseline and 3,6,9,12,18, 24,36
Lab results	Lab parameter LDH		Baseline
Status	Date of physical check-up		Status at Baseline

	Organ transplantation		

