##### **14.3.2.2 Secondary analysis**

All secondary outcomes will be analyzed descriptively.

The rate of ORR and 95%-confidence interval will be given for each cohort. In addition and in an exploratory way, the pooled rate and its 95%-confidence interval will also be given. Potential predictors of response will be analyzed using logistic regression and/or Factorial Multiple Correspondences Analyses.

For time to event parameters, Kaplan-Meier curves will be presented and median time to event will be estimated with corresponding 95%-confidence intervals.

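### Overall survival in the prospective cohort has no single time origin, and the origins before cemiplimab start build in death-free time unless delayed entry is applied

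*Protocol*

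**What the plan says.** **OS definition in the objectives and statistics sections.** Sections 6 and 14.3.1.2 use the same wording for the prospective cohort: "OS defined as duration from current mCSCC or ladvCSCC diagnosis and also from the initiation of each LOT", ending at death or the end of follow-up. This gives at least two origins, and more for a patient with several lines of therapy.

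**OS definition in the CRF table.** In Section 9 (parameters and definitions) the row is labelled "OS from diagnosis", but its definition runs from the first "Cemiplimab treatment until death from any cause, censoring for date of most recent follow-up in surviving patients".

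**Entry to the cohort.** Section 8.2 admits adults "who are at the first time initiated on Cemiplimab treatment according to SmPC of Cemiplimab". Section 7.1 says that at each site "all advCSCC patients who will initiate treatment with Cemiplimab in a real-world setting will be eligible to participate in the study". Section 7.2 adds: "In the prospective cohort the data will be recorded during a follow-up of 36 months, beginning after study inclusion".

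**Estimator.** Section 14.3.2.2: "For time to event parameters, Kaplan-Meier curves will be presented and median time to event will be estimated". Neither delayed entry nor left truncation is mentioned.

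**Neighbouring variables.** TTNT (Section 14.3.1.1) and prospective-cohort PFS (Section 14.3.1.2) both start at cemiplimab. The proportions surviving at months 3 to 36 start at the initiation of systemic therapy, without saying whether that means cemiplimab or an earlier agent. Prior systemic treatment is expected in this cohort and is collected.

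**The concern.** There are two separate problems.

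The first is one of definition. A programmer working from Section 14.3.1.2 and one working from the Section 9 table would report different OS medians under the same name. The Section 9 row also disagrees with its own label.

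The second is one of estimation. A patient who died between the advanced diagnosis and cemiplimab start, or during an earlier line, cannot be in the prospective cohort. If OS is counted from diagnosis or from a pre-cemiplimab line, and every patient is placed in the risk set from time zero, that interval contributes person-time in which no enrolled patient could have died. The direction of the error is known: survival is overstated.

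At stake is a reported secondary result, namely an OS median and curve for cemiplimab patients that look too favourable and that depend on which definition is programmed.

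**Working it through.** **Step 1: which origins are affected.** Entry is at first cemiplimab initiation.

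| Origin | Source | Death-free time by design? |
|---|---|---|
| Current mCSCC/ladvCSCC diagnosis | Sections 6, 14.3.1.2 | Yes, up to cemiplimab start |
| Line before cemiplimab | Sections 6, 14.3.1.2 (each line) | Yes, up to cemiplimab start |
| Cemiplimab line | Sections 6, 14.3.1.2 (each line); definition in the Section 9 row | No |
| Later line started under observation | Sections 6, 14.3.1.2 (each line) | No |
| Start of systemic therapy (survival proportions) | Sections 6, 14.3.1.2 | Yes, if an earlier agent is meant |

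**Step 2: inputs for the size.** The protocol states no OS figure, so there is nothing to reproduce. It gives neither the interval from diagnosis to cemiplimab nor an expected OS. Both are assumptions here: exponential OS from diagnosis with true median M = 18, 24 or 36 months, and lag to cemiplimab G = 3, 6 or 12 months.

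**Step 3: fixed lag.** With a constant hazard and everyone entering at G, the curve from diagnosis stays at 1.000 until G and its median is M + G. For M = 24 and G = 6, true survival at 6 months is 2^(-6/24) = 0.841. The curve shows 1.000, and the median reads 24 + 6 = 30 months.

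**Step 4: variable lag.** Death times and lags are drawn as exponentials (lag mean G), only patients alive at cemiplimab start are kept, and each is followed for 36 months after entry. The simulated Kaplan-Meier results are:

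| True median M | Mean lag G | Median from diagnosis, no delayed entry | Excess over M | 12-month survival shown | True 2^(-12/M) | Median from cemiplimab start |
|---|---|---|---|---|---|---|
| 18 | 3 | 20.9 | 2.9 | 0.702 | 0.630 | 18.1 |
| 18 | 6 | 23.2 | 5.2 | 0.753 | 0.630 | 18.0 |
| 18 | 12 | 26.8 | 8.8 | 0.813 | 0.630 | 17.9 |
| 24 | 3 | 26.7 | 2.7 | 0.768 | 0.707 | 23.9 |
| 24 | 6 | 29.6 | 5.6 | 0.810 | 0.707 | 24.0 |
| 24 | 12 | 33.9 | 9.9 | 0.867 | 0.707 | 24.2 |
| 36 | 3 | 38.8 | 2.8 | 0.837 | 0.794 | 35.8 |
| 36 | 6 | 41.5 | 5.5 | 0.872 | 0.794 | 35.7 |
| 36 | 12 | 46.3 | 10.3 | 0.909 | 0.794 | 35.5 |

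**Step 5: closed-form check of one row (M = 24, G = 6).** Let a = ln2/24 = 0.0289 be the death rate and b = 1/6 = 0.1667 the rate of starting cemiplimab. Among patients who live to start it,

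S*(t) = [exp(-at) - (a/(a+b)) exp(-(a+b)t)] / (b/(a+b)),

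with a/(a+b) = 0.1477 and b/(a+b) = 0.8523.

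- At 12 months: (0.7071 - 0.1477 × 0.0957)/0.8523 = 0.813, against 0.810 simulated.
- At the median the numerator must equal 0.5 × 0.8523 = 0.4262. This is met at t = 29.5 months (0.4266 - 0.0005 = 0.4261), against 29.6 simulated.

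The estimate from cemiplimab start returns the assumed median within simulation error, which locates the problem in the origin and risk set.

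**The case against.** **The unbiased origin is already in the plan.** Each line of therapy includes the cemiplimab line, and the definition in the Section 9 row is exactly that variant. This stands. The plan does not replace a sound OS with a biased one. It lists several, does not say which is the main one, and mislabels one.

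**Delayed entry belongs in the SAP.** Section 14.3.2.2 is compatible with a left-truncated Kaplan-Meier estimate, and a SAP that is not shown may specify it. This also stands, so the bias is conditional on no delayed entry being applied. A SAP method would not make Sections 6 and 14.3.1.2 agree with the Section 9 label.

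**The lag may be short.** The origin is the current diagnosis, and locally advanced disease is itself defined by a tumor-board decision that curative treatment is not possible. First-line patients treated soon after that decision add little guaranteed time. This is fair, and it is why the figures are only an illustration.

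**A stronger reading that a reader might infer** is that OS is overstated for cemiplimab relative to the retrospective cohort. The documents do not support it. Sections 6 and 14.3.1.3 give no OS origin for that cohort, and the synopsis merely names OS among its outcomes. The synopsis also describes those patients as treated before cemiplimab approval. If treatment is a condition of inclusion, their OS from diagnosis would contain a guaranteed interval too. No diagnosis-origin OS comparison between cohorts is specified, and Section 8.1 rules out hypothesis testing.

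**Conclusion.** The point holds in two parts. The inconsistency of the OS origin between Sections 6 and 14.3.1.2 and the Section 9 row, and between that row's label and its definition, is certain and needs no assumption. The upward bias holds for OS from diagnosis and from any pre-cemiplimab line, provided that the Kaplan-Meier estimate is run without delayed entry.

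The size cannot be taken from the protocol. Under the assumed exponential model with a constant hazard, true medians of 18 to 36 months and mean lags of 3 to 12 months, the excess in the median is about 3 to 10 months. Shorter lags give less.

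OS is a secondary, descriptive outcome. TTNT, cemiplimab-origin PFS and the sample size are unaffected. The change should be made because the definition alters a reported result, but the study does not depend on it.

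**What to change.** 1. In Sections 6, 9 and 14.3.1.2, name first cemiplimab treatment as the main OS origin for the prospective cohort.
2. Relabel the Section 9 row so that the name matches its definition.
3. State for the prospective cohort which start of systemic therapy the survival proportions at months 3 to 36 refer to.
4. If OS from diagnosis or from a pre-cemiplimab line is kept, call it supplementary and estimate it with left truncation, so that each patient joins the risk set at cemiplimab start. This assumes that time of entry is independent of prognosis, which should be stated.
5. Do not set such an estimate beside retrospective OS unless both cohorts use the same origin.

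**Cost.** Edits to three sections and a little extra analysis work. Diagnosis, therapy and death dates are already planned in the CRF. OS from diagnosis will look less favourable than the uncorrected curve.

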### **Secondary objectives of the retrospective cohort**

- Description of retrospective patient population, patterns of care and effectiveness of different treatment options used under routine conditions for advanced CSCC prior to Cemiplimab launch
- To collect and describe safety data on study participants
- Proportion of patients surviving at month 3, 6, 9, 12, 18, 24 and up to months 36 from initiation of systemic therapy
- PFS defined as time from first documented systemic therapy initiation until progression or treatment discontinuation due death or end of follow up
- Patient demographics and baseline characteristics (incl. age, performance status etc.) at study entry
- TNM stage (AJCC or UICC)
- Patterns of treatment for the retrospective cohort.

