#### **Study completion**

Prospective cohort: Each patient will be considered to have completed this study at the time they complete 3 years of follow up at the time they withdraw consent for further participation, or at the time of death.

Patients will remain in the study even if they discontinue cemiplimab permanently or temporarily.

Patients who discontinue treatment and/or choose not to continue with follow up visits and questionnaires will still be followed for survival at 3 month intervals, provided they do not withdraw their consent completely for the full 3 years duration of follow-up.

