#### **14.3.1.3 Secondary variables of the retrospective cohort**

- \* Characteristics of retrospective patient population, patterns of care and effectiveness of different treatment options used under routine conditions for advanced CSCC prior to Cemiplimab launch
- \* Safety data on study participants
- \* Proportion of patients surviving at month 3, 6, 9, 12, 18, 24 and up to months 36 from initiation of systemic therapy
- \* PFS defined as time from first documented systemic therapy initiation until progression or treatment discontinuation due death or end of follow up
- \* Patient demographics and baseline characteristics (incl. age, performance status etc.) at study entry
- \* TNM stage (AJCC or UICC)
- \* Patterns of treatment for the retrospective cohort.

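### The PFS definition in Sections 6 and 14.3.1 is garbled and contradicts the CRF table, so the reported PFS depends on which reading the analyst picks

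*Protocol*

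**What the plan says.** The Protocol defines PFS in five places.

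- Section 14.3.1.2 and the prospective list in Section 6: "PFS defined as time from first documented systemic cemiplimab therapy initiation until progression or treatment discontinuation due death or end of follow up".
- Section 14.3.1.3 and the retrospective list in Section 6: "PFS defined as time from first documented systemic therapy initiation until progression or treatment discontinuation due death or end of follow up".
- The CRF table in Section 9: "Defined as documented start of systemic Cemiplimab therapy until disease progression or death".

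Three other provisions bear on the point.

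- Patients are followed after treatment stops. Section 7.1 says "In case of Cemiplimab treatment discontinuation at any time, the documentation will continue until D8" or death, and Section 8.3 (study completion) adds that those who stop "will still be followed for survival at 3 month intervals".
- In the prospective cohort, stopping treatment has its own endpoint: "TTF including lack of response and discontinuation due to AE".
- For OS, the CRF table states the censoring rule: "censoring for date of most recent follow-up in surviving patients". The PFS row states none.

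Section 14.3.2.2 analyses time-to-event variables by Kaplan-Meier, with medians and 95% confidence intervals.

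**The concern.** The four statements in Sections 6 and 14.3.1 are not a usable event rule. The words between progression and end of follow-up can be read in two ways, and neither matches the CRF table.

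- **Reading 1 (literal).** PFS ends at progression, or when treatment stops because the patient died. A patient who stopped earlier, for toxicity or because therapy was complete, and then died without documented progression has no event.
- **Reading 2 (list).** Stopping treatment for any reason, death, and end of follow-up each end PFS. A patient who stops in remission is then counted as a PFS failure.

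Two analysts could report different PFS from the same data. The retrospective cohort is worse placed: the CRF row starts the clock at cemiplimab, so the garbled wording is the only PFS definition that cohort has, and the synopsis names PFS among its effectiveness outcomes.

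**Working it through.** **Plan's own figure.** The Protocol plans no PFS figure, so there is none to reproduce. Its only design calculation, the confidence interval for median TTNT, does not involve PFS.

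**Which deaths count, by rule**

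| Patient | CRF table | Reading 1 | Reading 2 |
|---|---|---|---|
| Progresses | event | event | event |
| Dies on treatment, no progression | event | event | event |
| Stops for another reason, later dies, no progression | event at death | no event | event at the stop |
| Stops for another reason, alive, no progression | no event | no event | event at the stop |

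The last two rows are where the rules part. Because follow-up runs on after treatment, such patients will be in the data.

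**Size, for illustration only.** The anchor is the 18.4-month PFS in 59 metastatic patients quoted in Section 5.1, taken as the median under the CRF definition. It is a background result and not a planning value for either cohort. Everything else here is assumed.

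*Reading 1, simple form.* With constant hazards and a share q of PFS events censored, the median is multiplied by 1/(1 − q).

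- q = 10%: 1/0.90 = 1.11, so 18.4 becomes 20.4 months.
- q = 20%: 1/0.80 = 1.25, so 18.4 becomes 23.0 months.

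*Readings 1 and 2 by simulation.* Exponential times, 400,000 draws, cut-off at 36 months. Deaths are assumed to be 10% to 40% of PFS events. Median time to stopping is assumed to be 12 or 24 months, independent of progression and death.

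| Deaths, % of events | Median time to stop (months) | Off-treatment deaths, % of events | Reading 1, those deaths censored | Reading 1, those deaths ignored | Reading 2 |
|---|---|---|---|---|---|
| 10 | 12 | 4.8 | 19.1 | 19.3 | 7.3 |
| 10 | 24 | 3.1 | 18.8 | 18.9 | 10.4 |
| 20 | 12 | 9.8 | 20.1 | 20.7 | 7.3 |
| 20 | 24 | 6.2 | 19.3 | 19.6 | 10.4 |
| 30 | 12 | 14.6 | 21.1 | 22.2 | 7.3 |
| 30 | 24 | 9.3 | 19.8 | 20.3 | 10.4 |
| 40 | 12 | 19.5 | 22.4 | 24.2 | 7.2 |
| 40 | 24 | 12.4 | 20.5 | 21.2 | 10.4 |

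Medians are in months. "Ignored" is shorthand here for keeping the patient at risk to month 36.

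The Reading 2 column can be checked by hand, since hazards add: 1/(1/18.4 + 1/12) = 7.3 and 1/(1/18.4 + 1/24) = 10.4.

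*End of follow-up as an event.* The PFS hazard is ln 2/18.4 = 0.0377 per month. Adding an assumed loss of 0.5%, 1% or 2% per month gives medians of 0.693/0.0427 = 16.2, 0.693/0.0477 = 14.5 and 0.693/0.0577 = 12.0 months.

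Against 18.4 months, Reading 1 therefore moves the median by +0.4 to +4.0 months (deaths censored) or +0.5 to +5.8 (ignored). Reading 2 moves it by about −8 to −11.

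**The case against.** The intent can be recovered. The CRF table is clear for cemiplimab, and Section 11.2.1 ends duration of response at progression or death. PFS is one of many secondary, descriptive endpoints, and detailed censoring rules normally sit in the statistical analysis plan. This limits the weight of the point but does not remove it: the Protocol does not leave the rule open, it states two that conflict. Nor does the CRF row help the retrospective cohort.

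Three stronger inferences are tempting, and the documents do not carry them.

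- *PFS is overstated.* This follows only from Reading 1. That is the closest literal reading, because the CRF table lists death among the coded reasons for stopping therapy, but the grammar is too broken to exclude Reading 2, which biases the other way.
- *End of follow-up is an event.* The OS definition in Section 14.3.1.2 also runs to end of follow-up, and the CRF table treats that as censoring. The phrase is probably shorthand. The text should say so.
- *The retrospective cohort is biased more, because its treatments are short and most deaths come later.* No passage gives treatment durations or the share of deaths without prior progression. Section 5.1 calls chemotherapy responses short-lived, so progression may often come first.

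**Conclusion.** The point holds as a contradiction and an ambiguity in a secondary endpoint, and the wording should be corrected. Followed literally, Sections 6 and 14.3.1 drop deaths that the study collects and that the CRF definition counts. Read the other way, they turn every treatment stop into a PFS event.

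Neither the direction nor the size of the error can be fixed from the documents. The figure of about 11% to 25% on the median assumes Reading 1, constant hazards, and 10% to 20% of PFS events being off-treatment deaths that are censored. The simulation, where such deaths fall later, gives slightly less for similar shares: 20.1 months at 9.8% and 22.4 at 19.5%, or about +9% and +22%. The share itself is assumed throughout. The primary endpoint and the sample size, both based on TTNT, are not affected.

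**What to change.** Put one definition in all five places (both lists in Section 6, Sections 14.3.1.2 and 14.3.1.3, and the CRF table), for example:

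> *PFS is the time from the start of the first documented systemic therapy (cemiplimab in the prospective cohort) to the first documented progression or death from any cause, whether on or off treatment. Stopping treatment is not in itself an event; in the prospective cohort it is covered by TTF. Patients with neither event are censored at the last documented visit at which they were progression-free.*

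Censoring at the last progression-free visit is preferable to censoring at the last tumour assessment. The CRF table records progression at each visit, but lists restaging and its date at baseline only, and the visit schedule has no dated row for tumour assessments.

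The cost is wording only. Date of progression, date of death and progression status by visit are already in the CRF table.
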